4.1 TREATMENT PLAN: Ribociclib

Ribociclib will be supplied by Novartis or its designee in the form of 200 mg hard gelatin capsules or tablets as individual patient supply packaged in bottles. Storage conditions are described in the medication label.

All dosages prescribed and dispensed to the patient and all dose changes during the study must be recorded.

Ribociclib will be administered as a flat-fixed dose of 600 mg daily, and not by body weight or body surface area.

Patients must be instructed to return unused study drugs to the site at discontinuation or completion of treatment. The site personnel must ensure that the appropriate dose of each study drug is administered and that the drug accountability is performed.

Ribociclib must be taken as follows:

- Patients should be instructed to take the ribociclib capsules/tablets with a large glass of water (~250 ml) at the same time each day.
- Ribociclib can be taken without regard to meals; however dietary habits around the time of dosing should be as consistent as possible throughout the study
- Patients should be instructed to swallow the ribociclib capsules/tablets whole and not to chew, crush or open them.
- If vomiting occurs during the course of treatment, no re-dosing of the patient is allowed before the next scheduled dose
- Any doses that are missed (not taken within 6 hours of the intended time) should be skipped and should not be replaced or made up on a subsequent day.
- Patients must avoid consumption of grapefruit, grapefruit hybrids, pummelos, star-fruit, Seville oranges or products containing the juice of each during the entire study and preferably 7 days before the first dose of study medication, due to potential CYP3A4 interaction with the study medications. Orange juice is allowed.
- No herbal or dietary supplements are permitted, due to potential interactions with ribociclib; multivitamins are allowed.

4.2 TREATMENT PLAN: Letrozole

Letrozole is formulated as tablets of 2.5 mg and supplied in bottles. The dose of letrozole is one 2.5 mg tablet administered orally once daily. The oral single dose of ribociblib should be taken together with the daily dose of letrozole 2.5 mg as per schedule below.

4.3 Treatment Dispensation, Compliance and Accountability

- 4.3.1 Ribociclib will be provided and dispensed by the pharmacy. Study medication will be supplied in an open label fashion. Patients will self-administer both medications at home.
- 4.3.2 Patients will be instructed to take the study medication at an approximately consistent time each day.

The use of a patient pill calendar (See Appendix C) during study therapy will be utilized by the patient and the treating clinic to help promote and monitor compliance with Ribociclib and letrozole.

4.4 Concomitant Medications

In general, the use of any concomitant medication deemed necessary for the care of the patient is permitted in this study, except as specifically prohibited below. Combination administration of study drugs could result in drug-drug interactions (DDI) that could potentially lead to reduced activity or enhanced toxicity of the concomitant medication and/or ribociclib.

The following lists are not comprehensive and are only meant to be used as a guide. The lists are based on the Oncology Clinical Pharmacology guidance, Drug-Drug Interaction and Comedication Consideration (v05, release date: 2015), which was compiled from the Indiana University School of Medicine's P450 Drug Interaction Table

(http://medicine.iupui.edu/clinpharm/ddis/main-table/) and supplemented with the FDA Draft Guidance for Industry, Drug Interaction Studies – Study Design, Data Analysis, and Implications for Dosing and Labeling (February 2012)

(http://www.fda.gov/downloads/drugs/guidancecomplianceregulatoryinformation/guidances/ucm292362.pdf), and the University of Washington's Drug Interaction Database (http://www.druginteractioninfo.org/). For current lists of medications that may cause QT prolongation and/or torsades de pointes (TdP), refer to the CredibleMeds® website (www.qtdrugs.org).

4.5 AGENTS (DRUG FORMULATION AND PROCUREMENT)

4.5.1 Investigational Agent: Ribociclib

Ribociclib will be supplied by Novartis or its designee in the form of 200 mg hard gelatin capsules or tablets as individual patient supply packaged in bottles. Storage conditions are described in the medication label.

All dosages prescribed and dispensed to the patient and all dose changes during the study must be recorded. Ribociclib will be administered as a flat-fixed dose (e.g. 400 mg or 600 mg daily), and not by body weight or body surface area.

Patients must be instructed to return unused study drugs to the site at discontinuation or completion of treatment. The site personnel must ensure that the appropriate dose of each study drug is administered and that the drug accountability is performed.

4.5.1.1 Source and Pharmacology: Also known by its tradename Kisqali® and its clinical trials name LEE011, is a kinase inhibitor indicated in combination with an aromatase inhibitor as initial endocrine-based therapy for the treatment of postmenopausal women with hormone receptor (HR)-positive, human epidermal growth factor receptor 2 (HER2)-negative advanced or metastatic breast cancer

4.5.1.2 Adverse Events and Drug Interactions

Most common adverse reactions (incidence ≥ 20%) are neutropenia, nausea, fatigue, diarrhea, leukopenia, alopecia, vomiting, constipation, headache and back pain.

See **Appendix D** for prohibited concomitant medications

Drugs known to prolong QT interval: Avoid concomitant use of drugs known to prolong QT interval such as anti-arrhythmic medicines.

4.5.1.3 Guidelines for Administration

Ribociclib must be taken as follows:

- Patients should be instructed to take the ribociclib capsules/tablets with a large glass of water (~250 ml) at the same time each day.
- Ribociclib can be taken without regard to meals; however dietary habits around the time of dosing should be as consistent as possible throughout the study
- Patients should be instructed to swallow the ribociclib capsules/tablets whole and not to chew, crush or open them.
- If vomiting occurs during the course of treatment, no re-dosing of the patient is allowed before the next scheduled dose
- Any doses that are missed (not taken within 6 hours of the intended time) should be skipped and should not be replaced or made up on a subsequent day.
- Patients must avoid consumption of grapefruit, grapefruit hybrids, pummelos, star-fruit, Seville oranges or products containing the juice of each during the entire study and preferably 7 days before the first dose of study medication, due to potential CYP3A4 interaction with the study medications. Orange juice is allowed.

• No herbal or dietary supplements are permitted, due to potential interactions with ribociclib; multivitamins are allowed.

4.5.1.4. Drug Supply and Storage

Please refer to the Regulatory Manual for Drug Ordering Instructions and Forms.

Study treatments must be received by designated personnel at the study site, handled and stored safely and properly, and kept in a secured location to which only the investigator and designated site personnel have access. Upon receipt, the study treatment should be stored according to the instructions specified on the medication label. Medication labels will comply with the legal requirements of each country and be printed in the local language.

Study Drug Compliance and Accountability

Compliance should be assessed by the investigator and/or study personnel at each patient visit and information provided by the patient and/or caregiver. Records of study medication used, dosages administered, and intervals between visits and the completion of the study should be captured in the Drug Accountability Form. This information must be captured in the source document at each patient visit.

4.5.2 Commercial Agent: Letrozole

4.5.2.1 Refer to the FDA-approved package insert for more information: https://dailymed.nlm.nih.gov/dailymed/drugInfo.cfm?setid=82b77d74-085f-45ac-a7dd-1f5c038bf406

4.5.2.2

Source and Pharmacology: Also known by its tradename Femara®, letrozole is an aromatase inhibitor indicated for adjuvant treatment of postmenopausal women with breast cancer.

4.5.2.3 Adverse Events and Drug Interactions

The most common adverse reactions (greater than 20%) were hot flashes, arthralgia; flushing, asthenia, edema, arthralgia, headache, dizziness, hypercholesterolemia, sweating increased, bone pain; and musculoskeletal.

4.5.2.4 Guidelines for Administration

Letrozole tablets are taken orally without regard to meals.

Recommended dose: 2.5.mg once daily.

Patients with cirrhosis or severe hepatic impairment: 2.5 mg every other day

4.5.2.5 Supplier: Letrozole will be supplied by Novartis or its designee. Please refer to the Regulatory Manual for drug ordering instructions and forms.

4.6 Safety Lead-in

A review of safety will occur after the first 6-10 patients are treated and complete one cycle (including starting cycle 2 within the DLT constraints below) or have a DLT prior to completing the first cycle. Within the safety lead-in, patients who do not have a DLT and who do not complete cycle 1 will be replaced.

A dose limiting toxicity (DLT) is defined as an AE or clinically significant abnormal laboratory value assessed as unrelated to disease, disease progression, inter-current illness, or concomitant medications that occurs within the first 28 days of treatment with ribociclib and meets any of the criteria included in the table below. NCI CTCAE version 5.0 should be used for all grading.

Criteria for Defining Dose-Limiting Toxicities

Toxicity	DLT Criteria
Hematology	CTCAE grade 4 neutropenia lasting more than 7 consecutive days
	CTCAE grade 4 thrombocytopenia
	CTCAE grade 3 thrombocytopenia with bleeding
	CTCAE grade 3 or 4 febrile neutropenia
ECG QT interval	QTc interval ≥501 ms on at least 2 separate ECGs
Cardiac	Cardiac toxicity ≥ CTCAE grade 3
	Clinical signs of cardiac disease, such as unstable angina or myocardial
	infarction, or Troponin ≥ CTCAE grade 3
Gastro-intestinal	≥ CTCAE grade 3 vomiting ≥48 hours despite optimal anti-emetic therapy
	≥ CTCAE grade 3 diarrhea ≥48 hours despite optimal anti-diarrhea treatment
Hepato-biliary	≥ CTCAE grade 2 total bilirubin for more than 7 consecutive days
	≥ CTCAE grade 3 total bilirubin
	≥ CTCAE grade 2 ALT with a ≥grade 2 bilirubin elevation of any duration
	in the absence of liver metastases
	≥ CTCAE grade 3 ALT for >4 consecutive days
	CTCAE grade 4 ALT or AST
	Grade 4 serum alkaline phosphatase >7 consecutive days
Renal	≥ CTCAE grade 3 serum creatinine

ILD/pneumonitis	≥ CTCAE grade 3	
Any drug-related death		
Non-hematologic events	≥ CTCAE grade 3, except for the exclusions noted below:	
Exceptions to DLT criteria	Grade 3 alopecia	
	<5 days of CTCAE grade 3 fatigue	
	Grade 3 fever or infection without neutropenia <5 days duration	
	Grade 3 laboratory abnormalities that are responsive to oral supplementation or deemed by the investigator to be clinically insignificant	

CTCAE version 5.0 should be used for grading.

Optimal therapy for vomiting and diarrhea should be based on institutional guidelines with consideration of the prohibited medications listed in these protocol guidelines.

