4.7.1.1 Ribociclib Dose Adjustment/Management Recommendation for Hematological Adverse Reactions

Toxicity/Grade	Dose Adjustment and Management Recommendations
Thrombocytopenia	
Grade 1(≥75 x10 ⁹ /L)	No dose adjustment required.

Grade 2 (≥50 x 10 ⁹ /L − <75 x 10 ⁹ /L)	Dose interruption until recovery to grade <2
	Re-initiate ribociclib at the same dose.
Grade 3 (≥25 x 10 ⁹ /L - <50 x 10 ⁹ /L)	Dose interruption until recovery to grade <2.
	Re-initiate ribociclib at the same dose level.
	If toxicity recurs at grade 3: temporary dose
	interruption until recovery to grade 1 and reduce
	ribociclib to the next lower dose level.
Grade 4(<25 x 10 ⁹ /L)	Dose interruption until recovery to grade <2.
	Re-initiate ribociclib at the next lower dose level.
	If toxicity recurs at grade 4: discontinue ribociclib
Absolute neutrophil count (ANC)	
Grade 1 (≥1.5 x10 ⁹ /L)	No dose adjustment required.
Grade 2 (≥1.0 - <1.5 x 10 ⁹ /L)	No dose adjustment required.
Grade 3 (≥0.5 - <1.0 x 10 ⁹ /L)	Dose interruption until recovery to $\geq 1.0 \times 10^9/L$.
	Re-initiate ribociclib at the same dose level.
	If toxicity recurs at grade 3: temporary dose
	interruption until recovery to ≥1.0 x 10 ⁹ /L.
	If resolved in ≤7 days, then maintain dose level.
	If resolved in >7 days, then reduce ribociclib dose
	to the next lower dose level.
Grade 4 (<0.5 x 10 ⁹ /L)	Dose interruption until recovery to ≥1.0 x 10 ⁹ /L.
	Re-initiate ribociclib at the next lower dose level.
	If toxicity recurs at grade 4: temporary dose
	interruption until
	recovery to ≥1.0 x 10 ⁹ /L and reduce ribociclib
	at the next lower dose level.

Febrile neutropenia	
Grade 3 ANC <1.0 x 10 ⁹ /L with a single temperature of >38.3 ^o C (101 ^o F) or a sustained temperature of ≥38 ^o C (100.4 ^o F) for more than one hour	Dose interruption until improvement of ANC ≥1.0 x 10 ⁹ /L and no fever. Restart at the next lower dose level. If febrile neutropenia recurs, discontinue ribociclib.
Grade 4	Discontinue ribociclib.

Life-threatening	
consequences; urgent	
intervention indicated	
Anemia	
(Hemoglobin)	
Grade 1 (≥10.0 – LLN g/dL)	No dose adjustment required.
Grade 2 (≥8.0 – <10.0 g/dL)	No dose adjustment required.
Grade 3 (<8.0 g/dL)	Dose interruption until recovery to grade <2.
	Re-initiate ribociclib at the same dose.
Grade 4	Discontinue ribociclib.
Life-threatening	
consequences; urgent	
intervention indicated	

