Increase from baseline grade 0 or 1 to grade 2 (>3.0 – 5.0 x ULN)	Dose interruption of ribociclib If resolved to ≤ baseline value in ≤21 days, then maintain dose level If resolved to ≤ baseline value in >21 days or toxicity recurs, then reduce 1 dose level Repeat liver enzymes and bilirubin tests twice weekly for 2 weeks after dose resumption If toxicity recurs after two dose reductions or recovery to ≤ baseline value is >28 days, discontinue ribociclib	
Increase from baseline grade 0 or 1 to grade 3 (>5.0 – 20.0 x ULN)	Dose interruption of ribociclib until resolved to ≤ baseline value, then lower 1 dose level of ribociclib Repeat liver enzymes and bilirubin tests twice weekly for 2 weeks after dose resumption If recovery to ≤ baseline value is >28 days, discontinue ribociclib If toxicity recurs, discontinue ribociclib	

Increase from baseline grade 2 to grade 3 (>5.0 – 20.0 x ULN)	Dose interruption of ribociclib until resolved to ≤ baseline value, then lower 1 dose level of ribociclib Repeat liver enzymes and bilirubin tests twice weekly for 2 weeks after dose resumption If toxicity reoccurs after 2 dose reductions or recovery to ≤ baseline value is > 28 days, discontinue ribociclib
Grade 4 (>20.0 x ULN)	Discontinue ribociclib
AST or ALT and concurrent Bilirubin	Discontinue Hibociciii
For patients with normal ALT or AST or total bilirubin at baseline: AST or ALT ≥ grade 2 combined with total bilirubin >2 x ULN without evidence of cholestasis or For patient with elevated AST or ALT or total bilirubin at baseline: baseline: [AST or ALT >2 x baseline AND >3.0x ULN] OR [AST or ALT 8.0x ULN]- whichever is lower-combined with [total bilirubin 2x baseline AND >2.0 x ULN]	

Confounding factors and/or alternative causes for increased transaminases should be excluded before dose interruption/reduction. They include but are not limited to: concomitant medications, herbal preparations or dietary supplements, infection, hepatobiliary disorder or obstruction, new or progressive liver metastasis, and alcohol intake.

Additional Follow-up for Hepatic Toxicities

Increase in transaminases combined with total bilirubin (TBIL) increase may be indicative of drug induced liver injury (DILI), and should be considered as clinically important events.

The threshold for potential DILI may depend on the patient's baseline AST/ALT and TBIL value; patients meeting any of the following criteria will require further follow-up as outlined below:

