For patients with normal ALT or AST or TBIL value at baseline: AST or ALT > 3.0 x
 ULN combined with TBIL > 2.0 x ULN

For patients with elevated AST or ALT or TBIL value at baseline: [AST or ALT > 2 x baseline AND > 3.0 x ULN] OR [AST or ALT > 8.0 x ULN], whichever is lower, combined with [TBIL > 2 x baseline AND > 2.0 x ULN]

Medical review needs to ensure that liver test elevations are not caused by cholestasis, defined as: ALP elevation > 2.0 x ULN with R value < 2 in patients without bone metastasis, or elevation of ALP liver fraction in patients with bone metastasis.

Note: (The R value is calculated by dividing the ALT by the ALP, using multiples of the ULN for both values. It denotes the relative pattern of ALT and/or ALP elevation is due to cholestatic or hepatocellular liver injury or mixed type injury)

In the absence of cholestasis, these patients should be immediately discontinued from study drug treatment, and repeat LFT testing as soon as possible, preferably within 48 hours from the awareness of the abnormal results. The evaluation should include laboratory tests, detailed history, physical assessment and the possibility of liver metastasis or new liver lesions, obstructions/compressions, etc.

Hepatic toxicity monitoring includes the following LFTs: albumin, ALT, AST, total bilirubin, direct and indirect bilirubin, alkaline phosphatase (fractionated if alkaline phosphatase is grade 2 or higher), creatine kinase, protrombine time (PT/INR) and GGT. For patients with Gilbert Syndrome: total and direct bilirubin must be monitored, intensified monitoring applies to changes in direct bilirubin only.

Close observation is recommended in case of AST, ALT, and/or bilirubin increase requiring dose interruption, which involves:

- Repeating liver enzyme and serum bilirubin tests two or three times weekly.
 Frequency of retesting can decrease to once a week or less if abnormalities stabilize or return to normal values.
- Obtaining a more detailed history of current symptoms.
- Obtaining a more detailed history of prior and/or concurrent diseases, including history of any preexisting liver conditions or risk factors.
- Obtaining a history of concomitant drug use (including non-prescription medications, herbal and dietary supplements), alcohol use, recreational drug use, and special diets.

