6.2 Evaluations on Treatment

Collection of Concomitant Medications and Adverse Events (AEs) should occur throughout the study, as described. Pre-treatment (Screening) evaluations do not need to be repeated if within 28 days of Cycle 1 Day 1.

Day 1 (±3 days)

- History and physical exam with vital signs
- Labs: CMP, CPK, CBC with differential (diff), Uric acid, Urinalysis
- If WOCBP, pregnancy test within 3 days of treatment for Cycle 1 only
- AEs

- ECG (if clinically indicated)
- Study drugs to be taken daily at the same time every day for 21-consecutive days.
- CA-125
- Lipid panel (total cholesterol, HDL, LDL, triglycerides) fasting preferred
- Coagulation (PT and INR)

Day 21 (±3 days)

- Ribociclib –start of 1-week off period.
- Letrozole Continue taking through the week off period of Ribociclib.
- 6.3 Off-Treatment Evaluations (End of Treatment or EOT visit)

The end of treatment visit will be performed as soon as possible but no later than 4 weeks (i.e., 28 days) $\pm 7 \text{ days}$ from last dose of investigational product and prior to the initiation of any new anticancer therapy.

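### Grade 4 anemia meets no DLT criterion in Section 4.6, although Section 4.7.1.1 stops ribociclib for it; a smaller AST gap sits in the combined liver row

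*Combined protocol and SAP*

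**What the plan says.** Section 4.6 defines a DLT as an adverse event or clinically significant laboratory abnormality in the first 28 days of ribociclib, not attributed to disease, intercurrent illness or other medication, that meets a row of the DLT table.

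- **Hematology rows.** Grade 4 neutropenia for more than 7 days, grade 4 thrombocytopenia, grade 3 thrombocytopenia with bleeding, and finally "CTCAE grade 3 or 4 febrile neutropenia". There is no anemia row.
- **Catch-all.** The row labelled for non-hematologic events reads "≥ CTCAE grade 3, except for the exclusions noted below".
- **Combined liver row.** "≥ CTCAE grade 2 ALT with a ≥grade 2 bilirubin elevation of any duration", in the absence of liver metastases. AST is not named.
- **Replacement.** In the lead-in, "patients who do not have a DLT and who do not complete cycle 1 will be replaced".

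Section 4.7.1.1 lists anemia among the hematological reactions, describes grade 4 as life-threatening, and says to "discontinue ribociclib". For patients with normal baseline values, Section 4.7.1.2 sets its combined liver trigger at "AST or ALT ≥ grade 2 combined with total bilirubin >2 x ULN without evidence of cholestasis". Its follow-up text adds: "In the absence of cholestasis, these patients should be immediately discontinued from study drug treatment".

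Section 11.3 takes x as the number of patients with a DLT and n as the number who had a DLT or were treated for a full cycle. The prior is Beta(2,6). Stopping is considered when Pr(θ > 0.25 | x, n) exceeds 0.5, which means 2 or more DLTs in 6 or 7 patients, or 3 or more in 8 to 10.

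**The concern.** The DLT table and the dose-modification table order the hematologic events differently. Grade 4 thrombocytopenia, and grade 4 neutropenia lasting more than 7 days, are DLTs, yet after a first occurrence Section 4.7.1.1 lets ribociclib restart one level lower. Grade 4 anemia ends ribociclib outright, yet it is not a DLT. The protocol gives no reason.

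Anemia is a plausible effect of this regimen. It was reported at any grade in 27.7% of the phase Ib doublet patients (Section 1.6), and in phase III it was 14.9 points more frequent than with placebo plus letrozole (Section 1.8). Patients may enter with hemoglobin of 9.0 g/dL, which Section 4.7.1.1 already places in grade 2.

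At stake is whether the pre-specified count, the only input to the Bayesian guideline, includes a life-threatening treatment-related event of the kind the lead-in exists to detect.

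**Working it through.** **Step 1. Does any row catch grade 4 anemia?** The hematology rows do not name it, and the catch-all is limited to non-hematologic events. It would count only if it led to another listed event, such as a grade 3 cardiac event or a drug-related death.

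**Step 2. Which AST events escape?** Section 4.7.1.2 puts grade 2 bilirubin at >1.5 to 3.0 x ULN and stops drug above 2 x ULN. Other rows of Section 4.6 already count bilirubin of grade 3 or higher, bilirubin of grade 2 or higher for more than 7 days, grade 4 AST, and grade 3 AST through the catch-all unless the investigator judges it clinically insignificant. What remains is AST of grade 2 (or a waived grade 3), ALT below grade 2, and bilirubin >2 to 3 x ULN for 7 days or less.

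**Step 3. Reproduce Table 11.1.** Pr(θ > 0.25 | x, n) = 1 − F(0.25; 2 + x, 6 + n − x), where F is the Beta distribution function. This reproduces the table; the only 0.01 difference is rounding at n=9, x=2 (0.405, printed as 0.41). Around the critical value r:

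| n | r | Posterior at x = r − 1 | Posterior at x = r |
|---|---|---|---|
| 6 | 2 | 0.333 | 0.584 |
| 7 | 2 | 0.281 | 0.521 |
| 8 | 3 | 0.461 | 0.686 |
| 9 | 3 | 0.405 | 0.630 |
| 10 | 3 | 0.353 | 0.574 |

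One uncounted event can therefore decide the guideline, but only when listed DLTs stand at r − 1 in the final n.

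**Step 4. Average effect.** Let p be the listed-DLT rate and q the rate of omitted events, taken as mutually exclusive. Both are assumptions.

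- Counted: P(Bin(n, p + q) ≥ r).
- Not counted, patient replaced: P(Bin(n, p/(1 − q)) ≥ r).

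Example, n=6, p=0.20, q=0.01. Counted: 1 − 0.79^6 − 6 × 0.21 × 0.79^5 = 0.369. Replaced: the same form with 0.20/0.99 = 0.2020 gives 0.350. The gap is 0.020.

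| n | p | Counted (q=0.01) | Replaced (q=0.01) | Gap |
|---|---|---|---|---|
| 6 | 0.10 | 0.134 | 0.116 | 0.018 |
| 6 | 0.20 | 0.369 | 0.350 | 0.020 |
| 10 | 0.20 | 0.353 | 0.328 | 0.024 |

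Over n=6 to 10 and p=0.10, 0.20 and 0.25, the gap at q=0.01 runs from 0.0096 (n=8, p=0.10) to 0.0242 (n=10, p=0.20). The same formulas give about 0.5 to 1.2 points at q=0.005 and 2.1 to 4.9 points at q=0.02.

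**Step 5. What the documents say about q.** They give no rate for grade 4 anemia in cycle 1. In the phase Ib doublet 2 of 47 patients (4.3%) discontinued for any adverse event at any time. In phase III the most common events leading to ribociclib discontinuation were raised ALT (4.5%), raised AST (2.7%) and vomiting (2.4%), not anemia. A small q is reasonable.

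**The case against.** **Stopping rules and DLT rules need not match.** Section 4.7 governs every cycle, and Section 4.6 is a short cycle-1 screen. Section 4.7.1.6 likewise stops treatment for grade 2 renal impairment, while a renal DLT needs grade 3 creatinine. This stands as a general point: a mismatch alone is not an error. It does not explain why anemia of any grade is absent when less decisive grade 4 cytopenias are listed.

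**The event would be seen.** A reader might infer that a life-threatening event could pass unnoticed. The documents do not support that. Serious events are reported within 24 hours (Section 10.1.5), the bi-weekly calls review adverse events and laboratory values (Section 10.3), and the critical values are guidelines subject to clinical judgment (Section 11.3). The purpose is also not to find an MTD. All of this stands and limits the consequence, but none of it changes the pre-specified x.

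**The patient might stay in n as a non-DLT.** A reader might infer this for an event first found at scheduled laboratory tests ("Labs: CMP, CPK, CBC with differential (diff), Uric acid, Urinalysis", done on Day 1 of each cycle), with letrozole continuing. The documents do not show it to be likely. Section 4.6 makes completing a cycle include starting cycle 2 within DLT constraints, and Section 11.3 brings cycle 2 delays into the DLT category, although neither gives a length. Cycle 2 Day 1 is nominally day 29, and an event arising after day 28 is outside the DLT window whatever the table lists. Replacement is the more natural reading, and counting her as a DLT is possible.

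**The liver gap is small.** A reader might infer that AST-driven liver injury generally escapes the count. Step 2 shows that it does not. In addition, Section 4.7.1.2 requires confirmed cases with no other cause to be reported as a serious event of potential drug-induced liver injury. If that event were graded 3 or higher, the catch-all could count it; the documents do not state its grade.

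**Conclusion.** The concern holds for grade 4 anemia: no row of Section 4.6 lists it, so a treatment-related case in the first 28 days is not a listed DLT although ribociclib is stopped. The patient would most likely be replaced, leaving both x and n, unless the undefined cycle 2 delay wording is taken to include her.

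The practical effect is small. It matters when listed DLTs are one below the critical value. The average loss in the chance of meeting the guideline is about 1.0 to 2.4 percentage points, which rests on an assumed 1% event rate, assumed listed-DLT rates of 10% to 25%, and replacement of the patient. The AST omission is a consistency matter confined to the window in Step 2.

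Nothing here calls Table 11.1 or the critical values into question. The case for acting is that the definition leaves out a life-threatening event and is very cheap to correct.

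**What to change.** Add CTCAE grade 4 anemia to the hematology rows of the DLT table in Section 4.6.

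As a minor consistency edit, write ALT or AST in place of ALT in the combined liver row.

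No separate replacement sentence is needed: once the event is listed the patient has a DLT, and Section 4.6 replaces only patients without one.

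The cost is a few words in one table, to be settled before the lead-in. The downside is that the stopping guideline is met slightly more often, by the 1.0 to 2.4 points above at an assumed 1% rate.
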